2.0	Changed recruitment time to: June 1, 2017 to February 28, 2018 Visit dates: now counted from date of embryo transfer instead of date of oocyte pick-up, leading to a reduction of figures by 5 for all visit dates, as day-5 blastocysts are being transferred. New visit (Visit 4) with US inserted at day 21 (+4/-3), range of visit at day 28 (Visit 5) changed to (+4/-3), at Visit 6 documentation of pregnancy category. Inclusion criteria: Also frozen day-5 blastocysts and egg donation permitted, maximum age increased to 45 years. Subsequently for exclusion criteria: egg donation deleted; term 'gestational surrogacy' specified.	May 09, 2017	[name], PhD [name] [name], MD

GLOSSARY OF ABBREVIATIONS

AE	Adverse Event
AUC	Area Under the Curve
eCRF	Electronic Case Report Form
ET	Embryo Transfer
EU	European
hCG	Hyperglycosylated human chorionic gonadotropin
IVF	In Vitro Fertilization
ROC	Receiver Operator Curve
US	Ultrasound

SYNOPSIS OF PROTOCOL

ACRONYM	HyperPOC (hyperglycosylated hCG Proof Of Concept study)
TITLE	Comparison of hhCG with hCG+ β in the early prediction of ongoing pregnancy after in-vitro fertilization and embryo transfer
STUDY NUMBER	1701-VLC-011-EB (CIM RD002786)
TRIAL CLASSIFICATION	Biomedical study
SPONSOR	IVI Valencia
STUDY AUTHORS	
[name] Director del Área de Medicina Reproductiva Unidad de Medicina Reproductiva, IVI Valencia [name] E-mail: [contact] Business [contact] ([name])
 
[name] Gobal Clinical Leader, Roche Diagnostics Centralised and Point of Care Solutions [name] Email: [contact] Business [contact]
 
[name] [name], Medical Director, IST GmbH [name] Email: [contact] Business [contact]

RESPONSIBLE CONTACT PERSONS	
Principal Investigator: [name]
 
[name], Roche Diagnostics Centralised and Point of Care Solutions
 
[name] [name], Medical Director, IST GmbH

SUPPORT FUNCTIONS	Biostatistics: [name], Prometris GmbH, Mannheim, Germany
PRODUCTS	hhCG (Quest Diagnostics), Elecsys [®] hCG+ β
INDICATION	Prediction of ongoing pregnancy in women undergoing IVF
STUDY DESIGN	Monocentric, prospective, open, biomedical study
STUDY PURPOSE SUMMARY	Proof of concept for the prediction of ongoing pregnancy in women undergoing IVF using hhCG

PRIMARY PURPOSE	Utility of the hhCG assay (Quest Diagnostics), early after In Vitro Fertilization and fresh or frozen Embryo Transfer (IVF-ET), as aid in the prediction of ongoing pregnancy
STUDY OBJECTIVES	
Primary objective:
 
To determine, based on the AUCs of the ROC curves, whether serum hyperglycosylated human chorionic gonadotropin (hhCG) measured on day 4 (+1) after ET* is superior to hCG+β measured on day 4 (+1) in predicting clinical pregnancy on day 21 (+4/-3) (=6 weeks after last menstruation, with detection of embryo sac by US).
 
*ET= Embryo Transfer; all days mentioned in the following are counted from ET (=Day 0).

	
Secondary objectives*:
 
 1. To determine, based on the AUC of the ROC curves, whether hhCG measured on day 7 (+1) and day 11 (+2) is superior to hCG+β measured on the same days in predicting clinical pregnancy on day 21 (+4/-3) 2. To determine, based on the AUC of the ROC curve, whether hhCG measured on day 4 (+1), day 7 (+1) and day 11 (+2) is superior to hCG+β measured on the same days in predicting ongoing pregnancy on day 65 (+7) . 3. To determine, based on the AUC of the ROC curve, whether hhCG measured on day 4 (+1) and day 7 (+1) is superior to hCG+β measured on the same days in predicting pregnancy on day 11 (+2) defined by serum hCG+β. 4. To compare the sensitivity and specificity and the positive and negative predictive value of hhCG with hCG+β measured on days 4 (+1), 7 (+1) and 11 (+2) for clinical pregnancy on day 21 (+4/-3) and ongoing pregnancy on day 65 (+7) and to identify cut-off values. 5. To compare the sensitivity and specificity and the positive and negative predictive value of hhCG with hCG+β measured on days 4 (+1) and 7 (+1) for pregnancy on day 11 (+2) defined by serum hCG+β and to identify cut-off values. 6. To determine, based on the AUCs of the ROC curves, whether changes in hhCG on day 7 (+1) vs. day 4 (+1) and day 11 (+2) vs. day 7 (+1) are superior to corresponding

	
changes in hCG+β in predicting clinical pregnancy on day 21 (+4/-3) and ongoing pregnancy on day 65 (+7).
 
 7. To determine, based on the AUCs of the ROC curves, whether changes in hhCG on day 7 (+1) vs. day 4 (+1) are superior to corresponding changes in hCG+β in predicting pregnancy on day 11 (+2) defined by serum hCG+β. 8. To compare the sensitivity and specificity and the positive and negative predictive value of changes in hhCG with those of hCG+β on day 7 (+1) vs. day 4 (+1) and day 11 (+2) vs. day 7 (+1) for clinical pregnancy on day 21 (+4/-3) and ongoing pregnancy on day 65 (+7). 9. To compare the sensitivity and specificity and the positive and negative predictive value of changes in hhCG with those of hCG+β on day 7 (+1) vs. day 4 (+1) for pregnancy on day 11 (+2) defined by serum hCG+β. 10. To determine the course of hhCG and hCG+β from day 4(+1) through day 11(+2) 11. To determine the usefulness of absolute values and changes in hhCG over time in distinguishing between the 5 disjunct pregnancy categories of 1) negative pregnancy, 2) ectopic pregnancy, 3) 1st trimester miscarriage 4) ongoing pregnancy on day 65 (+7) and 5) biochemical pregnancy. 12. To investigate into differences in the course of hhCG values between single and multiple pregnancies (if warranted by the number of multiple pregnancies) 13. To determine incidents and indirect harms. 
*All days mentioned above are counted from ET (=Day 0).

TARGET STUDY POPULATION	
Inclusion criteria:
 
 • Written informed consent • Patients undergoing their first or second IVF-ET cycle • Age 18-45 years • Use of Ovitrelle for final follicular maturation and luteinization in the case of fresh ET • Fresh or frozen day-5 blastocysts transfer (autologous or egg donation)

	
Exclusion criteria:
 
 • Gestational surrogacy (patient's eggs used for pregnancy in a surrogate mother) • Canceled IVF cycles • GnRH agonist triggering cycles in the case of fresh ET
STUDY DURATION PLANNED	
Clinical part of the study: from June 2017 to April 2018
 
Patient recruitment time: from June 1, 2017 to Dec 31, 2017

STUDY POPULATION & TOTAL NUMBER OF PATIENTS	
A sample size of n= 136 patients eligible for the per-protocol analysis has been calculated of whom n=61 are expected to present with clinical pregnancy on day 21* (+4/-3). Based on an assumed rate of 10% patients enrolled but ineligible for the per-protocol analysis, n=152 patients are planned to be included in the study.
 
*Counted from ET (=Day 0).

NO. OF SITES	Monocentric study
SCHEDULE OF ASSESSMENTS	See Schedule of Assessments below
SAFETY	
As the only impact on patient safety by the study is from taking two additional blood samples, a general AE collection and assessment will not be carried out. Any AEs occurring in temporal relationship to drawing the two blood samples in addition to the study site's clinical routine will be documented observing the rights of patients' compensation for damage through participation in the study and the requirements of the insurance policy taken out. Incidents in connection with the diagnostic test will be documented following EU and local regulations and guidelines. Indirect harms to the patients are not possible to occur as the test result will only be known after individual study end. Hence, any incorrect results of the test can have no consequence for the further course of the patient during the study.

COMPLIANCE STATEMENT	
The study will be conducted in compliance with the Guidelines for Good Pharmacoepidemiology Practices (GPP) and applicable regulatory requirements.

Schedule of Assessments

	Screening	Visit 1	Visit 2	Visit 3	Visit 4	Visit 5	Visit 6
Days from ET ¹		Day 4 (+1)	Day 7 (+1)	Day 11 (+2)	Day 21 (+4/-3)	Day 28 (+4/-3)	Day 65 (+7)
Patient information	●						
Informed consent ²	●						
Demogr. data, Med. hist. ³	●						
Body weight and height	●						
Concomitant diseases	●	●	●	●	●	●	
Concomitant medication	●	●	●	●	●	●	
Incl. / excl. criteria	●						
Number of embryos transferred	●						
Serum estradiol, progesterone		●	●	●			
(Serum) hhCG, hCG+β ⁴		●	●	●			
Ultrasound ⁵					●	●	
Pregnancy category							●
Incidents and indirect harms							●
Final documentation ⁶							●

1 Embryo Transfer = day 0

2 Leaving the patient ample time for consideration after patient information has taken place

3 Including previous pregnancies and complications/outcomes

1 INTRODUCTION

1.1 hhCG Method Description

Serum samples will be collected and shipped on dry ice to Quest Diagnostics (Quest Diagnostics, Nichols Institute, San Juan Capistrano, CA) for measurements of hhCG. The ultrasensitive hhCG assay will be performed using a procedure described by Pandian et al. [1]. hhCG will be measured using an electrochemiluminescence (ECL) technique on 96-well plates from Meso Scale Discovery. This immunometric assay uses the hhCG specific antibody B-152 as the coating antibody and the hCG+ β beta specific antibody B-207 as the labeled antibody with Sulfo-Tag (Meso Scale Discovery). The light signal (relative light unit, RLU) generated by the antibody-antigen and antibody reaction will be measured by a luminometer (Meso Scale Discovery). The RLU is directly proportional to the concentration of hhCG.

1.2 Background and Study Rationale

1.2.1 Background

Hyperglycosylated human chorionic gonadotropin (hhCG) as it was later called was first isolated from the urine of women with invasive trophoblastic disease [2]. It is a hyperglycosylated isoform of human chorionic gonadotropin (hCG) with more extensive and more complex carbohydrate moieties than hCG during the initial 3 weeks of pregnancy hhCG is the primary hCG isoform [3–9]. It is synthesized primarily by cytотrophoblasts, whereas hCG is produced by syncytiotrophoblasts [12, 13]. hhCG is supposed to be of relevance during implantation into the uterine wall [13–15]. The monoclonal antibody against hhCG, B152, has a specificity for hhCG of >99 % relative to hCG [4, 8, 10], whereas many other antibodies against hCG show significant cross reactivity with hhCG [11].

Urinary hhCG levels during pregnancy were shown to rise 3 days sooner on average than those of hCG. The ratio of hhCG to hCG may allow to differentiate between clinical and biochemical pregnancy [5].

In a retrospective monocenter evaluation in 112 women with in vitro fertilization (IVF), fresh embryo transfer (ET) and day-9 and day-16 after egg retrieval (equals days 4 and 11 after ET) serum samples carried out by Chuan et al. it was found that a day-9 hhCG level of >110 pg/mL was 96% specific for ongoing pregnancy, yielding a positive predictive value of 94%. Compared with the day-9 hCG level, hhCG was more sensitive and had a larger area under the curve (0.87 vs. 0.67, respectively). In contrast, the diagnostic test characteristics were similar between the day-16 hhCG and hCG levels [16]. In a prospective blinded clinical trial by Strom et al. enrolling 58 IVF-ET patients a single serum or urine hhCG measurement identified pregnancies (both biochemical and clinical) on day 6 post ET with 100% sensitivity and specificity, whereby it was possible to identify biochemical pregnancies by their lower hhCG values [17].

1.2.2 Study Rationale

Proceeding on the results of previous clinical studies and particularly of the two studies by Chuan and Strom mentioned above [16, 17], it is a logical further step to try and validate the hypothesis of a superior predictive value of hhCG vs. hCG early after IVF-ET for clinical and ongoing pregnancy in a prospective study sufficiently powered based on existing data for the two diagnostic tests. The nature of the study is therefore that of a proof of concept trial.

1.3 Study Objectives

See Study Synopsis.

2 STUDY DESIGN AND ASSESSMENTS

2.1 Overview of Study Design

The study has been planned considering the principles of evidence based medicine using the PICO criteria [18]. It is a monocenter, open, biomedical study in patients undergoing in-vitro fertilization. The purpose of proof of concept requires keeping variability within very narrow limits. Accordingly, there is a strict definition of the selection criteria for patients to be enrolled, and the primary analysis will be carried out in the per protocol population.

It is planned to include a total of 152 patients. The study protocol is based on routine procedures at the site, with the only additional measures stipulated being the taking of 6-mL venous blood samples on visits 1 and 2 and the asservation of another 6-mL of venous blood on visit 3 when blood is taken anyhow within the scope of clinical routine. The three 6-mL blood samples will be processed for central assessment of hhCG. Neither the patient nor the investigator will know the result of the centralized analysis prior to individual study completion. Apart from the two blood samples mentioned there are only two further procedures involving the patients directly. This refers to the ultrasound assessments at visit 4 and the final visit for the assessment of clinical and ongoing pregnancy (both part of the study site's routine measures).

2.1.1 Blinding of Study

The study will be conducted in an open fashion. However, results of the hhCG assessments will only become available after study end.

2.1.2 Scope of Study

The study data will serve for a proof-of-concept evaluation.

2.2 In-/Exclusion Criteria

See Study Synopsis.

2.3 Patient Recruitment

Patients will be screened in a consecutive, unselected manner, and, after written informed consent has been obtained, will be eligible to be enrolled in the study if all inclusion and none of the exclusion criteria are met.

2.4 Data Collection

For an overview see Schedule of Assessments in the Protocol Synopsis.

Patients will only be included into the study after they have given their informed consent in writing. The study will begin with a Screening phase starting with Patient information and Patient's Informed Consent (leaving the patient ample time for consideration after Patient Information) and followed by the documentation of general patient data. On the basis of available data the decision as to the patient's eligibility to participate in the study will then be made considering the inclusion/exclusion criteria. In the case of eligible patients a total of five visits (planned in accordance with clinical routine) will follow during a period of a maximum of 68 days starting with day 4(+1) after ET (= Day 0).

As compared with clinical routine an additional 6 mL of blood is planned to be taken on each visit 1-3 (on Visit 3 a blood sample is drawn anyhow following clinical routine). Hence, the total amount of blood taken for the purpose of the study will be 18 mL (not considering the small amounts of blood needed for measuring serum estradiol and progesterone by IVI for visits 1 and 2). During visits 1 - 3 an aliquot of 0.5 mL of serum will be stored for the central assessment of hhCG by Quest Diagnostics, 0.5 mL for potential future biomarker analyses by IVI and another 2.0 mL for shipment to Roche potentially to be used for repeat measurements or measurements within the scope of developing a new hhCG immunoassay. Apart from this, there will be no further study-related measures with a potential impact on the patient's health and well-being. The US assessments at Visit 4 and 5 are part of clinical routine assessments.

Therefore, a general AE collection and assessment will not be carried out. Any AEs occurring in temporal relationship to drawing the two blood samples in addition to the study site's clinical routine will be documented on paper forms observing the rights of patients' compensation for damage through participation in the study and the requirements of the insurance policy taken out. Concomitant diseases and medication will be documented at each visit. Any changes from previous visits found, however, will not be followed up as a possible indication of an adverse event. Incidents in connection with the diagnostic test will be documented following EU and local regulations and guidelines. This will be done on a paper form and the information will not be entered into the eCRF. Indirect harms to the patients are not possible to occur as results of the central hhCG analyses will only be known to the study site after study end. Hence, any incorrect results of the hhCG test can have no consequences for the further course of the patient during the study.

Screening Phase

- Patient information
- Patient's informed consent
- Demographic data (race, ethnicity, age)
- Medical history including history of previous pregnancies and their outcomes and complications
- Body weight and height
- Concomitant diseases and medication
- Check of inclusion and exclusion criteria
- Number of embryos transferred and dates of oocyte pick-up, fertilization and ET

Visit 1

At Visit 1 the following will be done and documented in the eCRF:

- Measurement and documentation of serum estradiol, progesterone and hCG+ß values by the study site
- Taking of 6 mL of venous blood for asservation of 0.5 mL of serum (to be kept in the freezer at -80°C with temperature log and shipped in batches for the central analysis of hhCG), of a further 0.5 mL for IVI kept in the freezer at -80°C and another 2.0 mL serum kept in the freezer at -80°C to be shipped to Roche at the end of the study.
- Concomitant diseases and medication.

Visit 2

At Visit 2 the following will be done and documented in the eCRF:

- Measurement and documentation of serum estradiol, progesterone and hCG+ß values by the study site
- Taking of a further 6 mL of venous blood for asservation of 0.5 mL of serum (to be kept in the freezer at -80°C with temperature log and shipped in batches for the central analysis of hhCG), of a further 0.5 mL for IVI kept in the freezer at -80°C and of another of 2.0 mL kept in the freezer at -80°C for to be shipped to Roche at the end of the study.
- Concomitant diseases and medication.

Visit 3

At Visit 3 the following will be done and documented in the eCRF:

- Measurement and documentation of serum estradiol, progesterone and hCG+ß by the study site
- Separation of 6 mL of blood taken in addition to routine blood sampling for asservation of 0.5 mL of serum (to be kept in the freezer at -80°C with temperature log and shipped in batches for the central analysis of hhCG), of a further 0.5 mL for IVI kept in the freezer at -80°C and of another 2.0 mL kept in the freezer at -80°C for to be shipped to Roche at the end of the study.
- Concomitant diseases and medication.

Visit 4

At Visit 4 the following will be done and documented in the eCRF:

- Concomitant diseases and medication
- Ultrasound for detection of embryo sac, (heart beat) or ectopic pregnancy.

Visit 5

At Visit 4 the following will be done and documented in the eCRF:

- Concomitant diseases and medication
- Ultrasound for detection of embryo sac, heart beat or ectopic pregnancy.

Visit 6

At Visit 5 the following will be done and documented in the eCRF:

- Concomitant diseases and medication
- Documentation of pregnancy category: negative pregnancy, ectopic pregnancy, 1st trimester miscarriage, ongoing pregnancy (single/multiple) on day 65 (+7), biochemical pregnancy (see section 5.1)
- Incidents and indirect harms
- Final documentation.

2.5 Endpoints of the Study

2.5.1 Primary Endpoint

AUC of the ROC curve for hhCG and hCG+β on day 4 (+1) after ET for the prediction of clinical pregnancy on day 21 (+4/-3) after ET (=6 weeks after last menstruation, detection of embryo sac by US).

2.5.2 Secondary Endpoints

See also Section 5 for definitions. Secondary endpoints of the study are*:

1. AUC of the ROC curve for hhCG and hCG+β on days 7 (+1) and 11 (+2) for the prediction of clinical pregnancy on day 21 (+4/-3)
2. AUC of the ROC curve for hhCG and hCG+β on days 4 (+1), 7 (+1) and 11 (+2) for the prediction of ongoing pregnancy on day 65 (+7)
3. AUC of the ROC curve for hhCG and hCG+β on days 4 (+1) and 7 (+1) for the prediction of pregnancy on day 11 (+2) defined by serum hCG+β.
4. Sensitivity and specificity and positive and negative predictive value of hhCG and hCG+β on days 4 (+1), 7 (+1) and 11 (+2) for clinical pregnancy on day 21 (+4/-3)
5. Sensitivity and specificity and positive and negative predictive value of hhCG and hCG+β on days 4 (+1), 7 (+1) and 11 (+2) for ongoing pregnancy on day 65 (+7)
6. Sensitivity and specificity and positive and negative predictive value of hhCG and hCG+β on days 4 (+1) and 7 (+1) for pregnancy on day 11 (+2) defined by serum hCG+β
7. AUC of the ROC curve for changes in hhCG and hCG+β on day 7 (+1) vs. day 4 (+1) and on day 11 (+2) vs. day 7 (+1) for the prediction of clinical pregnancy on day 21 (+4/-3)

8. AUC of the ROC curve for changes in hhCG and hCG+β on day 7 (+1) vs. day 4 (+1) and on day 11 (+2) vs. day 7 (+1) for the prediction of ongoing pregnancy on day 65 (+7)
9. AUC of the ROC curve for changes in hhCG and hCG+β on day 7 (+1) vs. day 4 (+1) for the prediction of pregnancy on day 11 (+2) defined by serum hCG+β
10. Sensitivity and specificity and positive and negative predictive value of changes in hhCG and hCG+β on day 7 (+1) vs. day 4 (+1) and on day 11 (+2) vs. day 7 (+1) for the prediction of clinical pregnancy on day 21 (+4/-3)
11. Sensitivity and specificity and positive and negative predictive value of changes in hhCG and hCG+β on day 7 (+1) vs. day 4 (+1) and on day 11 (+2) vs. day 7 (+1) for the prediction of ongoing pregnancy on day 65 (+7)
12. Sensitivity and specificity and positive and negative predictive value of changes in hhCG and hCG+β on day 11 (+2) vs. day 7 (+1) for the prediction of pregnancy on day 11 (+2) defined by serum hCG+β
13. Absolute values and changes vs. previous visits of hhCG and hCG+β for course of the variables during the study
14. Absolute values and changes vs. previous visits of hhCG and hCG+β for the distinction of outcomes 1) negative pregnancy, 2) ectopic pregnancy, 3) 1st trimester miscarriage 4) ongoing pregnancy on day 65 (+7) and 5) biochemical pregnancy.
15. Absolute values and changes vs. previous visits of hhCG and hCG+β for the distinction between single and multiple pregnancies
16. Course of serum estradiol and progesterone during the study
17. Any AEs with a temporal relationship with drawing the two blood samples in addition to the site's clinical routine
18. Incidents involved with hhCG testing.

*All days mentioned in this section are counted from ET (=Day 0).

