5.1 Pregnancy Endpoints

The study will have to use various pregnancy endpoints for various analyses. For the analysis of the primary objective and some of the secondary objectives the endpoint will be clinical pregnancy on day 21* (+4/-3) defined as detection of embryo sac by US, regardless of whether or not there will be a miscarriage during the later course of the 1st trimester. For some other secondary objectives the endpoint will be ongoing pregnancy on day 65 (+7) defined as detection of fetal heart beat by US at this time point or later). Detection of embryo sac/fetal heart beat on day 65 (+7) replaces missing detection of embryo sac on day 21 (+4/-3) for the definition of clinical pregnancy.

For pregnancy on day 11 (+2) as an individual endpoint and for the allocation of patients to categories as described below (negative and biochemical pregnancy in particular) a cut-off value for hCG+β on day 11 (+2) of >10 mIU/mL will be used as per practice at the study site.

For the purposes of the analysis with respect to secondary objective no. 11 there will be 5 disjunct pregnancy categories:

1) Negative pregnancy

hCG+β on day 11 (+2) ≤10 mIU/mL, unless clinical pregnancy, ectopic pregnancy, ongoing pregnancy or 1st trimester miscarriage are detected at a later stage

2) Ectopic pregnancy

Rules out the remaining categories 3), 4) and 5)

3) 1st trimester miscarriage

Rules out (supersedes) categories 4) and 5)

4) Ongoing pregnancy on day 65 (+7)

5) Biochemical pregnancy

hCG+ β >10 mIU/mL on day 11 (+2) and no clinical/ongoing pregnancy at any stage and no ectopic pregnancy and no signs or symptoms of a 1st trimester miscarriage.

The following patients are ineligible for the analysis with respect to secondary objective no. 11: hCG+ β on day 11 (+2) >10 mIU/mL, missing data on ectopic pregnancy/ presence of embryo sac, fetal heart beat and no 1st trimester miscarriage.

1st trimester miscarriage will always be assumed in cases with detection of embryo sac on day 21 (+4/-3) and no ongoing pregnancy on day 65 (+7). It should be noted that per-protocol patients with this constellation will be included in the group of subjects with clinical pregnancy on day 21 (+4/-3) for the primary analysis of the study.

*All days mentioned in this section are counted from ET (=Day 0).

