7.6.2 Secondary Study Objectives

In addition to the comparison of the AUCs under the ROC curves for day 4*, the same analyses will be performed for the hhCG and hCG + β tests at days 7 and 11 with respect to predicting clinical pregnancy on day 21*; at days 4, 7 and 11 with respect to predicting pregnancy on day 65; at days 4 and 7 with respect to predicting pregnancy on day 11. The same methods as for the analysis of the primary objective will be applied here.

For the comparisons of sensitivity and specificity and the positive and negative predictive values at various time points with respect to pregnancy at various later time points, the following approach will be used:

Optimal thresholds for the two tests and the various time points will be identified from the pertinent ROC curves for the time point (day 4, 7 or 11) and endpoint (pregnancy at day 65,

21 or 11) considered. The optimal threshold for the time point and test at hand will be found using Youden's index (sensitivity + specificity -1), choosing the point for which the index is maximal.

The thresholds and the corresponding sensitivities and specificities will be summarized for each time point, pregnancy endpoint and test. Pertinent positive and negative predictive values will be shown for the same thresholds for the various time points.

The course of hhCG and hCG + β over time will be summarized by descriptive summary statistics (mean, standard error of the mean, median, Q1, Q3, minimum and maximum) for the disjoint pregnancy outcome categories as defined in 5.1. If there are sufficiently many multiple pregnancies, the same analysis will be performed for the categories of multiple and single pregnancies (irrespective of pregnancy outcome).

Incidents and indirect harms will be summarized by absolute and relative frequencies.

*All days mentioned in this section are counted from ET (=Day 0).

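### Secondary endpoint 12 uses the day-11 vs day-7 change to predict a day-11 outcome that the same day-11 hCG+β value defines, and it contradicts objective 9, which specifies day 7 vs day 4.

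*Combined protocol and SAP*

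**What the plan says.** Section 2.5.2, item 12, sets as an endpoint the sensitivity, specificity, PPV and NPV of the change given as "hhCG and hCG+β on day 11 (+2) vs. day 7 (+1) for the prediction of pregnancy on day 11 (+2) defined by serum hCG+β".

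Synopsis objective 9, the only objective with these measures, changes as predictors and this outcome, compares "changes in hhCG with those of hCG+β on day 7 (+1) vs. day 4 (+1) for pregnancy on day 11 (+2) defined by serum hCG+β".

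Section 5.1 fixes the outcome: for pregnancy on day 11, "a cut-off value for hCG+β on day 11 (+2) of >10 mIU/mL will be used as per practice at the study site". A value of 10 mIU/mL or less is negative.

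The AUC items for changes use the earlier interval. Objective 7 asks whether "changes in hhCG on day 7 (+1) vs. day 4 (+1) are superior to corresponding changes in hCG+β in predicting pregnancy", and endpoint 9 covers hhCG and "hCG+β on day 7 (+1) vs. day 4 (+1) for the prediction of pregnancy on day 11 (+2) defined by serum hCG+β". In section 7.6.2 the AUC comparisons for this outcome are made "at days 4 and 7 with respect to predicting pregnancy on day 11".

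**The concern.** There are two faults in one line.

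First, the endpoint does not serve its objective. Objective 9 and item 12 share the accuracy measures and the outcome but name different intervals. As written, objective 9 has no accuracy endpoint and item 12 has no objective behind it.

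Second, the interval in item 12 reaches the day on which the outcome is determined. The day-11 hCG+β result enters the hCG+β predictor and also decides who counts as pregnant. The hhCG change comes from the same blood draw but a different assay, so it has no such built-in link. A table comparing the two would show an advantage for hCG+β that comes partly from the definition. Both columns would describe same-day classification, because the outcome is already known once the day-11 hCG+β result is available.

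An analyst programming from section 2.5.2 would produce that table and leave out the one objective 9 asks for. Choosing between the two once data are in hand would be an avoidable post hoc decision.

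**Working it through.** The plan gives no figure on this point to reproduce. The check is a comparison of the text followed by short algebra.

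**Step 1. Every statement that pairs predictors with the day-11 hCG+β outcome**

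| Place | Measure | Predictor |
|---|---|---|
| Objective 3 | AUC | values on days 4, 7 |
| Endpoint 3 | AUC | values on days 4, 7 |
| Section 7.6.2, AUC sentence | AUC | values on days 4, 7 |
| Objective 5 | accuracy measures | values on days 4, 7 |
| Endpoint 6 | accuracy measures | values on days 4, 7 |
| Objective 7 | AUC | change, day 7 vs 4 |
| Endpoint 9 | AUC | change, day 7 vs 4 |
| Objective 9 | accuracy measures | change, day 7 vs 4 |
| **Endpoint 12** | accuracy measures | **change, day 11 vs 7** |

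Count: 4 objectives + 4 endpoints + 1 sentence = 9. Eight use only days 4 and 7.

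The day-11 vs day-7 change does have a proper place in the plan. Objectives 6 and 8 and endpoints 7, 8, 10 and 11 use it for the day-21 and day-65 outcomes, which lie after day 11. Carrying that interval over from items 10 and 11 would explain item 12, though the documents do not say so.

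**Step 2. The shared value, if change is a difference**

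Let H7 and H11 be hCG+β on days 7 and 11, with H7 ≥ 0.

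- Outcome positive: H11 > 10. Outcome negative: H11 ≤ 10 (section 5.1).
- Item 12 predictor: D = H11 − H7.
- In an outcome-negative patient, D ≤ 10 − H7 ≤ 10 − 0 = 10 mIU/mL.

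Section 7.4 counts values above the cut-off as positive. With a cut-off c ≥ 10, D > c forces H11 > 10 + H7 ≥ 10, so false positives are impossible:

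- Specificity = TN/(TN + 0) = 100%.
- PPV = TP/(TP + 0) = 100%, provided at least one patient tests positive.

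Section 7.6.2 sets thresholds by the maximum Youden index, so the cut-off is not known in advance. Below 10 mIU/mL, neither 100% figure is guaranteed.

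**Step 3. The shared value, if change is a ratio**

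The largest ratio H11/H7 in an outcome-negative patient is 10/H7. The plan gives no day-7 values, so those below are assumed:

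| Assumed H7 (mIU/mL) | 0.1 | 0.5 | 1 | 2 | 5 |
|---|---|---|---|---|---|
| 10/H7 | 100 | 20 | 10 | 5 | 2 |

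There is no fixed bound, so no accuracy figure is forced. The day-11 value still appears in both predictor and outcome.

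**Step 4. The interval in objective 9**

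For H7 − H4, with H4 the day-4 value, neither term enters the outcome definition. The definition therefore puts no limit on that change in outcome-negative patients. The hhCG change over either interval is also free of the defining value; over day 11 vs day 7 it is simply measured on the day of the outcome.

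**The case against.** The best case for leaving this alone is that it is a copying slip with little consequence.

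- **The right analysis can be recovered.** Section 1.3 sends the reader to the synopsis, where objective 9 is clear. Endpoint 9 already requires the ROC curve for the day-7 vs day-4 change against this outcome, so objective 9 needs only a readout from a planned curve. That is true, and it limits the damage, but the endpoint list still prescribes a different variable.
- **No decision hangs on it.** Section 7.6.2 plans to summarise sensitivities, specificities and predictive values, with no test specified for them. Any built-in advantage goes to hCG+β, so it could not create a false claim for hhCG. Both points stand and keep the severity down.
- **The size of the advantage is not shown.** Also true. The overlap is certain, but the 100% result depends on a difference and a cut-off of at least 10 mIU/mL, neither of which the plan fixes.
- **The count of nine leaves out a sentence.** The threshold paragraph in section 7.6.2 lists time points (day 4, 7 or 11) and outcomes (day 65, 21 or 11) together. Read literally, it would allow day 11 for day 11. But it assigns no particular predictor to an outcome and does not mention changes, so it neither supports item 12 nor settles the conflict. The count covers explicit pairings only.

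**Conclusion.** The point holds and should be fixed. Item 12 contradicts objective 9, and its hCG+β arm uses the outcome-defining value as part of the predictor. Both findings follow from the text alone; neither depends on an assumed effect size.

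The reach is small: 1 of 18 secondary endpoints, and 1 of 9 explicit pairings with the day-11 outcome. The primary endpoint, the sample size of 136 evaluable patients and the one-sided 2.5% level are untouched. The direction of the tilt, towards hCG+β, follows from the shared value. Its size cannot be stated, because the plan does not say whether change is a difference or a ratio and the cut-off will be chosen from the data.

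**What to change.** In section 2.5.2, item 12, replace the interval day 11 (+2) vs day 7 (+1) with day 7 (+1) vs day 4 (+1), and leave the measures and outcome as they are. The item then matches objective 9 and sits beside endpoint 9 as its accuracy counterpart.

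The cost is a one-line protocol correction. The day-4 and day-7 samples are already taken at Visits 1 and 2, so no visit, sample or data item is added.

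This edit does not settle whether change means a difference or a ratio, or how section 7.6.2 sets thresholds for changes. Those gaps affect the change analyses generally (objectives 6 to 9) and need their own clarification.
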